Metabolism appears to be the major route of elimination for ixazomib, and urinary excretion of the parent drug is negligible (< 5% of dose). In vitro studies indicate that ixazomib is metabolized by multiple cytochrome P450s (CYPs) and non-CYP enzymes/proteins. The rank order of relative biotransformation activity of the 5 major human CYP isozymes was 3A4 (34.2%) > 1A2 (30.7%)> 2D6 (14.7%) > 2C9 (12.1%) > 2C19 (< 1%). Ixazomib is not an inhibitor of CYPs 1A2, 2C9, 2C19, 2D6, or 3A4 nor a time-dependent inhibitor of CYP3A4/5. The potential for ixazomib treatment to produce drug-drug interactions (DDIs) via CYP inhibition is inferred to be low. However, there may be a potential for DDIs with a concomitant strong CYP3A4 or CYP1A2 inhibitor or inducer because of the potential for first-pass metabolism when ixazomib is administered via the PO route and because of the moderate contribution of CYP3A4- and CYP1A2-mediated metabolism of ixazomib in human liver microsomes. Ixazomib may be a weak substrate of P-glycoprotein (Pgp), breast cancer resistance protein (BCRP), and multidrug resistance associated protein (MRP2) efflux pump transporters. Ixazomib is not an inhibitor of Pgp, BCRP, and MRP2. The potential for DDIs with substrates or inhibitors of Pgp, BCRP, and MRP2 is, therefore, inferred to be low. Clinical Study C16009 (Arm 1) with ketoconazole, a strong CYP3A4 inhibitor, showed a 2-fold increase in area under the plasma concentration versus time curve (AUC) in the presence of ketoconazole. This resulted in the continued exclusion of strong CYP3A4 inhibitors in ongoing/planned clinical studies.

Further details on these studies are provided in the IB.

| Table 4  | Clinical Studies of Oral Ixazomib  |  |
|--|--|--|
| Trial/
Population                           | Description  | Doses Investigated   |
| C16003
RRMM
N = 60                | PO, TW, single agent   | 0.24-2.23 mg/m  TW
MTD: 2.0 mg/m 
DLT: rash, thrombocytopenia
Closed to enrollment  |
| C16004
RRMM
N = 60                | PO, W, single agent  | 0.24-3.95 mg/m  W
MTD: 2.97 mg/m 
DLT: rash, nausea, vomiting, diarrhea
Closed to enrollment  |

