#### 2.14 Potential Risks and Benefits

Please refer to the current ixazomib IB and SMA.

The clinical benefit of ixazomib continues to be studied in a comprehensive and global development plan that involves studies sponsored by Millennium. Ixazomib appears to show early signs of anti-tumor activity as evidenced by at least 50% reduction in disease burden in some patients, including patients that have been heavily pretreated as well as those with newly diagnosed MM, and prolongs stabilization of the underlying disease in other patients across all ongoing trials. The preliminary findings are favorable when considering historical and currently available therapies for the patient populations evaluated. Though additional data are needed to characterize the clinical benefit of this drug, the emerging data supports expanded development of ixazomib for the treatment of patients with advanced malignancy. This study will be conducted in compliance with the protocol, good clinical practice (GCP), applicable regulatory requirements, and International Conference on Harmonisation (ICH) guidelines.

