- 3.2.12 Systemic treatment, within 14 days before the first dose of ixazomib with strong CYP3A inducers (rifampin, rifapentine, rifabutin, carbamazepine, phenytoin, phenobarbital), or use of Ginkgo biloba or St. John's wort.
- 3.2.13 Known GI disease or GI procedure that could interfere with the oral absorption or tolerance of ixazomib including difficulty swallowing.
- 3.2.14 Grade 2 peripheral neuropathy or higher or grade 1 with pain on clinical examination during the screening period.
- 3.2.15 Participation in other clinical trials, including those with other investigational agents not included in this trial, within 30 days of the start of this trial and throughout the duration of this trial.
- 3.2.16 Previous treatment with ixazomib, or participation in a study with ixazomib whether treated with ixazomib or not.

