- Systemic treatment with any of the following metabolizing enzyme inducers should be avoided, unless there is no appropriate alternative medication for the patient's use (Rationale: If there were to be a DDI with an inducer, ixazomib exposure would be less; therefore, there would be a reduced chance of an AE. However, there may be less chance for an antitumor effect, but that is not an absolute reason to be taken off ixazomib):
  - Strong CYP3A inducers: rifampin, rifapentine, rifabutin, carbamazepine, phenytoin, and phenobarbital
  - Excluded foods and dietary supplements include St. John's Wort and Ginkgo Biloba
- The following procedures are prohibited during the study.
  - Any antineoplastic treatment with activity against MM, other than study drugs
  - Radiation therapy (note that, in general, the requirement for local radiation therapy indicates disease progression)

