#### Treatment modifications due to Ixazomib or lenalidomide-related AEs are outlined in Tables **11 and 12**.

| I able 11: Ixazomib and Lenalidomide Dose Adjustments for Hematologic Toxicities
Within-Cycle Dose Modifications (other than Day 1)                        |  |  |  |  |  |
|---|--|--|--|--|--|
| Criteria  | Action   |  |  |  |  |
| Platelet count ≤ 30,000/µL  | 
 
Ixazomib dose should be held. Lenalidomide dose should be held.
 
Complete blood count (CBC) with differential should be repeated at least every other day until the ANC and/or platelet counts have exceeded the pre-specified values on at least 2 occasions.
 
   |  |  |  |  |
| or
ANC ≤ 500/µL  | • Upon recovery (1 st occurrence), lenalidomide may be reinitiated with 1 dose level reduction depending on the attribution of the toxicity to the study agent. Do not dose reduce ixazomib. Upon recurrence of the toxicity (2 nd occurrence), ixazomib may be reinitiated with 1 dose level reduction depending on the attribution of the toxicity to the study agent.   |  |  |  |  |
| Dose Modifications  | for Subsequent Treatment Cycles on Day 1   |  |  |  |  |
| Criteria  | Action   |  |  |  |  |
| Delay of > 2 weeks in the start of a
subsequent cycle due to lack of
toxicity recovery as defined in
Section 6.3.1
ANC < 1,000/µL
Platelet count < 75,000/µL | 
 
Hold ixazomib and lenalidomide until resolution as per criteria Section 6.1.
 
Upon recovery, reduce lenalidomide 1 dose level, depending on the attribution of the toxicity to the study agent. If lenalidomide has been reduced during the cycle, consider a dose reduction of ixazomib upon reinitiating the subsequent cycle.
 
The maximum delay before treatment should be discontinued will be 3 weeks or at the discretion of the PI.
 
  |  |  |  |  |
| Dose Modifica   | tions for Subsequent Treatment Cycles  |  |  |  |  |
| Criteria  | Action   |  |  |  |  |

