| All Hematologic Toxicities  | 
 
For any hematologic toxicity that occurs during a cycle but recovers in time for the start of the next cycle:
 
If dose was reduced within the cycle, start the next cycle at that same dose.
 
If due to toxicity timing, ie, after Day 15 dosing thus a dose reduction was not required at that point in the cycle, reduce ixazomib by 1 dose level at the start of that cycle.
 
Do not reduce the dose both within a cycle and at the start of the cycle for the same most severe toxicity.
 
 |  |  |  |  |

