### Table 11: Ixazomib and Lenalidomide Dose Adjustments for Hematologic Toxicities

| Adverse Event   | Severity  | Action on Study Drug  | Further Considerations  |
|---|---|---|---|
|   | Grade 1
Peripheral
Neuropathy                               | No action   | Grade 1 signs and symptoms:
asymptomatic; without pain or
loss of function; clinical or
diagnostic observations only
deep tendon reflexes or
parasthesia |
| New or
Worsening
Peripheral
Neuropathy | Grade 1
Peripheral
Neuropathy
with pain
or
Grade 2 | Hold Ixazomib until resolution to Grade $\leq 1$ without pain or baseline   | Grade 2 signs and symptoms:
Moderate symptoms; limiting
instrumental activities of daily
living (ADL)  |
| (CTCAE v.4.0)   | Grade 2
Peripheral
Neuropathy
with pain
or
Grade 3 | Hold Ixazomib until
resolution to Grade ≤ 1
without pain or baseline
Reduce study drug to next
lower dose upon recovery   | Grade 3 signs and symptoms:
severe symptoms; limiting
self-care ADL; assistive
device indicated  |
|   | Grade 4
Peripheral
Neuropathy                               | Discontinue Ixazomib  | Grade 4 signs and symptoms:
Life threatening
consequences; urgent
intervention indicated   |
| Rash  | Grade 2   | Symptomatic
recommendations as per
section 5.3 and 5.4  |   |
| Non-Hematologic   |   | Hold Ixazomib or
lenalidomide depending on
the attribution until
resolution to Grade < 1 or
baseline  |   |
| toxicities judged
to be related to
study drug                         | Grade 3   | If not recovered to < Grade
1 or baseline within 3
weeks:
Reduce Ixazomib or
lenalidomide depending on
the attribution to next
lower dose upon return to
< Grade 1 or baseline | Symptomatic
recommendations noted in
Section 5.3 and 5.4  |

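### Section 2.8 reports that a strong CYP3A4 inhibitor doubles ixazomib exposure, but the trial's interaction rules (3.2.12 and 5.3.1) cover only inducers and two herbal products, and no reason is given

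*Combined protocol and SAP*

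**What the plan says.** Section 2.8 names a possible interaction with strong CYP3A4 or CYP1A2 inhibitors as well as inducers. It then reports that Study C16009 (Arm 1) "showed a 2-fold increase in area under the plasma concentration versus time curve (AUC) in the presence of ketoconazole", and that the consequence was the "continued exclusion of strong CYP3A4 inhibitors in ongoing/planned clinical studies".

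The operative text deals with inducers only. Exclusion 3.2.12 bars systemic treatment "within 14 days before the first dose of ixazomib with strong CYP3A inducers", lists six drugs, and adds Ginkgo biloba and St. John's wort. For the treatment period, 5.3.1 says: "Systemic treatment with any of the following metabolizing enzyme inducers should be avoided, unless there is no appropriate alternative medication". It lists the same six drugs and the same two supplements. Its rationale concerns reduced ixazomib exposure only.

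For risks and benefits, 2.14 defers to documents outside the protocol: "Please refer to the current ixazomib IB and SMA".

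**The concern.** The background and the operative rules disagree about one drug class. A site that finds an explicit interaction list limited to inducers could reasonably conclude that inhibitors are acceptable, although the same protocol says one of them doubles exposure.

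The omission is also on the less cautious side. Section 5.3.1 reasons that lower exposure means fewer adverse events and possibly less antitumour effect. By the same logic, higher exposure means more adverse events, yet only the drugs that lower exposure are listed. The patients have no symptomatic myeloma, so avoidable toxicity weighs heavily. In maintenance they may attend only every three cycles with a three-month ixazomib supply (5.1), so an inhibitor started between visits could go unnoticed.

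**Working it through.** **1. Text comparison**

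| Section | Inducers | Strong CYP3A4 inhibitors |
|---|---|---|
| 2.8 (background) | named as an interaction risk | named as a risk; AUC doubled with ketoconazole; class excluded in programme studies |
| 3.2.12 (entry) | six drugs and two herbal products excluded | not mentioned |
| 5.3.1 (on study) | same six drugs to be avoided; same two supplements excluded | not mentioned |
| Rest of 3.2, 5.3, 5.4, 6, 8.1 | no further rule | no restriction and no dose adjustment |

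No sentence expressly permits an inhibitor, and none bars or limits one. The permission is by omission.

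**2. Would the dose-modification rules make up for it?** Only in part, because the tabulated rules act after toxicity has appeared.

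- First within-cycle haematologic event (Table 11): both drugs are held, then "Do not dose reduce ixazomib".
- Grade 1 neuropathy with pain, or grade 2 without (Table 12): hold only.
- Other related grade 3 non-haematologic toxicity (Table 12): hold, with a reduction only if it has not recovered within 3 weeks.
- A reduction does follow for grade 2 neuropathy with pain or grade 3 neuropathy ("Reduce study drug to next" lower dose, Table 12), for grade 3 rash (5.4), and for haematologic toxicity after Day 15 dosing ("reduce ixazomib by 1 dose level at the start of that cycle", Table 11).

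So a patient could resume 4 mg with the interaction still present. Alternatively, a temporary co-medication could cause a reduction that may not be reversed (6.1) and that carries from induction into maintenance (Table 8). These rules are general and were not written with inhibitors in mind.

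**3. Illustration of size for one inhibitor**

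Inputs: ixazomib 4 mg (5.1); AUC ratio 2 (2.8); maximum tolerated dose (MTD) with lenalidomide and dexamethasone 2.97 mg/m² (2.7.2), about 5.5 mg fixed (Table 4 footnote).

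- Assuming dose-proportional exposure, which the documents do not state: 4 × 2 = 8 mg, and 8 / 5.5 = 1.45 times the MTD equivalent.
- Assuming AUC proportional to dose^b, the equivalent dose is 4 × 2^(1/b). With b = 0.8: 4 × 2.378 = 9.51 mg, and 9.51 / 5.5 = 1.73. With b = 1.2: 4 × 1.782 = 7.13 mg, and 7.13 / 5.5 = 1.30.
- For reference, three dose-limiting events occurred at 3.95 mg/m² (2.7.2). The footnote's ratios convert this to 3.95 × 3.0/1.68 = 7.05 mg up to 3.95 × 5.5/2.97 = 7.31 mg.

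**4. Patients affected.** The documents give no rate of inhibitor use. At an assumed 1% to 5% of 56: 0.01 × 56 = 0.56 and 0.05 × 56 = 2.8.

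**5. Design figures.** The sample size (53 eligible, 56 enrolled; 50% against 70% progression-free at 2 years) does not depend on co-medication. Nothing in section 13 changes.

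**The case against.** The strongest reply is that 2.8 is old programme text and that the inducer-only rule is deliberate. There is support for this:

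- Neighbouring ixazomib data are cut at 27 March 2013, and Table 5 is sourced to edition 7 of the IB, while this protocol version is dated 04 October 2019.
- Section 7.2.1.1 contains a cross-reference to a Section 6.7 that this protocol does not have, a sign of imported text.
- 3.2.12 and 5.3.1 agree with each other, and 5.3.1 gives a reasoned rationale, so the authors did consider CYP3A interactions.
- The 2.8 sentence describes other studies. It is not a rule of this investigator-initiated trial, and 2.8 itself points to the IB for details.

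This stands as far as it goes: the documents cannot show which text is current. It does not remove the mismatch, because no reason for leaving inhibitors out is given, and a pointer to the IB or SMA is neither an eligibility rule nor a concomitant-medication rule. If the authors did drop the restriction, then 2.8 is what needs correcting.

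Two smaller replies also carry some weight. Exclusions 3.2.5 (active infection) and 3.2.8 (HIV, HBV, HCV) would keep out some patients who might be on such drugs at entry, though not those who start one later. Section 6.1 also lets the investigator discuss ixazomib dose changes with the Principal Investigator without expressly requiring prior toxicity. That route is discretionary and gives no prompt about inhibitors.

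Three stronger readings are tempting. A reader might infer that the trial has a proven safety defect. The documents do not show that, since the inhibitor restriction may have been superseded. A reader might infer that such patients would be dosed above the MTD. That rests on assumed exposure scaling and one inhibitor, and it compares with an MTD set under repeated dosing, whereas a short inhibitor course might overlap only one or two weekly doses. A reader might also extend the point to strong CYP1A2 inhibitors. Section 2.8 mentions them as a possibility but reports neither a measured effect nor an exclusion.

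**Conclusion.** The inconsistency is established from the text: 2.8 reports a doubled AUC and a class exclusion, and the trial's own rules leave that class unrestricted without explanation. Whether this is a real safety gap is not established. It depends on the current IB and SMA, which are not among the documents, so it should be treated as a potential gap.

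The size is modest. Probably fewer than three patients would be affected, on an assumed rate of use, and the primary analysis and sample size are unaffected. The 8 mg and MTD comparison is an illustration under assumed dose-proportionality. It explains why the question deserves an answer and is not an estimate of harm. The point still merits action, because the disagreement concerns doubled exposure in asymptomatic patients and is cheap to settle.

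**What to change.** Check the current IB and SMA, then make one of two changes.

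- **Restriction still current, or not shown to be superseded:** add systemic strong CYP3A4 inhibitors to the 5.3.1 list of drugs to be avoided unless no suitable alternative exists, with a sentence on raised exposure beside the existing one on lowered exposure. Beside 3.2.12, add the same check for the 14 days before the first ixazomib dose: identify any strong CYP3A4 inhibitor and substitute it where possible. A firm entry exclusion goes further than the documents support.
- **Restriction superseded:** leave 3.2.12 and 5.3.1 as they are, correct the 2.8 sentence, and state the reason.

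The cost is one document check and a few lines of wording. The downside of the first option is that a few patients may need a substitute drug. No statistical section changes.

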#### **Clinical Trial Experience Using the Oral Formulation of Ixazomib** 2.9

As of 27 March 2013, a total of 507 patients with differing malignancies (multiple myeloma, AL amyloidosis, nonhematologic cancers, and lymphoma) have been treated in studies evaluating the oral ixazomib formulation. These patients have been treated with different doses of ixazomib either as a single-agent treatment (in 201 patients) or in combination with currently clinically available treatments (in 306 patients). Information regarding the ongoing studies, patient populations, and doses investigated is included in Table 4.

#### **Overview of the Oral Formulation of Ixazomib**

The emerging safety profile indicates that ixazomib is generally well tolerated. The adverse events (AEs) are consistent with the class-based effects of proteasome inhibition and are similar to what has been previously reported with VELCADE though the severity of some, for example peripheral neuropathy, is less. While some of these potential toxicities may be severe, they can be managed by clinical monitoring and standard medical intervention, or, as needed, dose modification or discontinuation.

In the 4 ongoing studies (C16003, C16004, C16007, and C16009) investigating single-agent oral ixazomib in patients with differing malignancies (multiple myeloma, AL amyloidosis, nonhematologic cancers, and lymphoma), a total of 201 patients have been treated as of 27 March 2013. These patients have been treated with different doses of ixazomib as they are all phase 1 trials. An overview of the most frequent (at least 10%) AEs occurring in the pooled safety population from single-agent oral ixazomib studies (C16003, C16004, C16007, and C16009) are shown in Table 5.

| Primary System Organ Class
Preferred Term         | Oral Single Agent
Total
n = 201
n (%) |
|--|--|
| Subjects with at Least One Adverse Event             | 197 (98)                                       |
| Gastrointestinal disorders                           | 160 (80)                                       |
| Nausea   | 106 (53)                                       |
| Diarrhoea  | 88 (44)  |
| Vomiting   | 77 (38)  |
| Constipation   | 46 (23)  |
| Abdominal pain                                       | 33 (16)  |
| General disorders and administration site conditions | 151 (75)                                       |
| Fatigue  | 103 (51)                                       |
| Pyrexia  | 51 (25)  |
| Oedema peripheral                                    | 27 (13)  |
| Asthenia   | 31 (15)  |
| Nervous system disorders                             | 92 (46)  |
| Headache   | 29 (14)  |
| Dizziness  | 26 (13)  |
| Neuropathy peripheral                                | 21 (10)  |
| Metabolism and nutrition disorders                   | 107 (53)                                       |
| Decreased appetite                                   | 64 (32)  |
|  |  |

Table 5Most Common (At Least 10% of Total) Treatment-Emergent Adverse Events in
Oral Single-Agent Studies

| Primary System Organ Class
Preferred Term    | Oral Single Agent
Total
n = 201
n (%) |
|---|--|
| Dehydration                                     | 37 (18)  |
| Blood and lymphatic system disorders            | 98 (49)  |
| Thrombocytopenia                                | 68 (34)  |
| Anaemia   | 42 (21)  |
| Neutropenia                                     | 29 (14)  |
| Lymphopenia                                     | 20 (10)  |
| Skin and subcutaneous tissue disorders          | 90 (45)  |
| Rash macular a                       | 23 (11)  |
| Musculoskeletal and connective tissue disorders | 93 (46)  |
| Back pain                                       | 24 (12)  |
| Arthralgia                                      | 28 (14)  |
| Respiratory, thoracic and mediastinal disorders | 78 (39)  |
| Cough   | 28 (14)  |
| Dyspnoea  | 30 (15)  |
| Infections and infestations                     | 89 (44)  |
| Upper respiratory tract infection               | 31 (15)  |

Table 5Most Common (At Least 10% of Total) Treatment-Emergent Adverse Events in
Oral Single-Agent Studies

Source: Ixazomib Investigator's Brochure Edition 7

Abbreviations: MedDRA = Medical Dictionary for Regulatory Activities, version 15.0.

Subject Incidence: A subject counts once for each preferred term. Percentages use the number of treated subjects as the denominator.

a. Note that rash maculopapular and rash macular represent the 2 most common terms used to describe rash.

As of 27 March 2013, there are 5 studies actively enrolling patients with multiple myeloma to investigate oral ixazomib in combination with standard combination regimens.

The most frequent (at least 10%) AEs occurring in the pooled safety population from Studies C16005, C16006, C16008, and C16013 are shown for all grades (Table 4). Note that in combination trials, related is defined as related to any study drug in the combination regimen.

| Table 6  | Most Common (At Least 10% of Total) Treatment-Emergent Adverse Events in |
|----------|--|
| Oral Com | ubination Studies  |

| Primary System Organ Class
Preferred Term         | Total Oral Combo Agent
(5/6/8/13)
n = 173
n (%) |  |
|--|--|--|
| Subjects with at Least One Adverse Event             | 163 (94)   |  |
| Gastrointestinal disorders                           | 139 (80)   |  |
| Nausea   | 65 (38)  |  |
| Diarrhoea  | 81 (47)  |  |
| Vomiting   | 51 (29)  |  |
| Constipation   | 57 (33)  |  |
| General disorders and administration site conditions | 132 (76)   |  |
| Fatigue  | 76 (44)  |  |
| Pyrexia  | 39 (23)  |  |
| Oedema peripheral                                    | 61 (35)  |  |
| Asthenia   | 20 (12)  |  |
| Nervous system disorders                             | 115 (66)   |  |
| Headache   | 28 (16)  |  |
| Dizziness  | 34 (20)  |  |
| Neuropathy peripheral                                | 45 (26)  |  |
| Metabolism and nutrition disorders                   | 91 (53)  |  |
| Decreased appetite                                   | 25 (14)  |  |
| Hypokalaemia   | 34 (20)  |  |
| Blood and lymphatic system disorders                 | 88 (51)  |  |
| Thrombocytopenia                                     | 49 (28)  |  |
| Anaemia  | 45 (26)  |  |
| Neutropenia  | 43 (25)  |  |
| Lymphopenia  | 20 (12)  |  |
| Skin and subcutaneous tissue disorders               | 102 (59)   |  |
| Rash maculopapular a                      | 29 (17)  |  |
| Rash macular a                            | 22 (13)  |  |
| Musculoskeletal and connective tissue disorders      | 99 (57)  |  |
| Back pain  | 42 (24)  |  |
| Pain in extremity                                    | 31 (18)  |  |
| Arthralgia   | 22 (13)  |  |
| Respiratory, thoracic and mediastinal disorders      | 80 (46)  |  |

| Primary System Organ Class
Preferred Term | Total Oral Combo Agent
(5/6/8/13)
n = 173
n (%) |
|--|---|
| Cough  | 36 (21)   |
| Dyspnoea                                     | 26 (15)   |
| Infections and infestations                  | 92 (53)   |
| Upper respiratory tract infection            | 35 (20)   |
| Psychiatric disorders                        | 73 (42)   |
| Insomnia                                     | 50 (29)   |

Table 6Most Common (At Least 10% of Total) Treatment-Emergent Adverse Events in
Oral Combination Studies

The clinical experience with ixazomib also shows early signs of antitumor activity as evidenced by at least a 50% reduction in disease burden in some patients and prolonged disease stabilization in others across all ongoing trials. The antitumor activity has been seen with single-agent ixazomib, when combined with established therapies, and across the malignancies studied (advanced solid tumors, non-Hodgkin's disease, Hodgkin's disease, relapsed and/or refractory multiple myeloma [RRMM, relapsed or refractory systemic light chain amyloidosis [RRAL], and newly diagnosed multiple myeloma [NDMM] to date.

Though additional data are needed to characterize the clinical benefit of this drug, the emerging data supports the ongoing development of ixazomib.

